6.2.10. Concentration-Time Data

PART A:

Blood samples for pharmacokinetic analysis of PK10571 will be collected at 0 hour (predose), and then at 3, 10, 20, 30, 40 minutes, and 1, 2, 4, 8, 12, 24, 36, and 48 hours after study treatment administration as specified by the protocol amendment. For two blood samples were collected at 1 and 5 minutes, instead of one blood sample at 3 minutes, prior to the protocol amendment. For and above, the 3-minute sample was collected after the protocol amendment.

PART B:

If QD dosing: Blood samples for pharmacokinetic evaluation will be obtained prior to the first dose administration (predose) on Day 1 and Day 7, and at the following times: Day 1 and Day 7 at 3, 10, 20, 30, and 40 minutes and 1, 2, 4, 8, 12, 24, and 36 hours after dosing; predose on Days 3-6, and on Day 8, Day 9, Day 10, Day 14, and Day 35 (total 34 samples).

If BID dosing: Blood samples for pharmacokinetic evaluation will be obtained prior to the first dose administration (predose) on Day 1 and Day 7, and at the following times after each dose (2 per day) on Day 1 and Day 7: 3 and 30 minutes and 2, 8, and 12 hours. Blood samples will also be collected before the first dose on Days 3-6, and on Day 8, Day 9, Day 10, Day 14, and Day 35 (total of 30 samples).

If TID dosing: Blood samples for pharmacokinetic evaluation will be obtained prior to the first dose administration (predose) on Day 1 and Day 7, and at the following times after each dose (3 per day) on Day 1 and Day 7: 3 and 40 minutes and 6 hours. An additional sample will be obtained on Day 2 (12 hours after the 3rd dose on Day 1). Blood samples will also be collected before the first dose on Days 2-6, and on Day 8 (6 hours and 12 hours after the 3rd dose on Day 7), Day 9, Day 10, Day 14, and Day 35 (total of 30 samples).

For multi-capsule administrations (if required to achieve the dose), the first postdose blood collection will be performed 5 minutes after the start of study treatment administration.

For summarization of the concentration-time data, concentrations below the limit of quantitation (BLQ) will be set to zero. Mean concentration-time profiles will be created for SAD (all cohorts), SAD male vs. female (all cohorts), MAD (all cohorts), MAD male vs. female (all cohorts), and MAD (Day 1 vs. Day 7) for each cohort. Mean concentration-time profiles will be created using nominal time. All subject concentration-time plots (all subjects in one plot for each cohort, SAD and MAD) will be created using actual time. Individual subject plots (one subject per plot) will be created for MAD (Day 1 vs. Day 7) using actual time.

For time points occurring before 1.00 hour, nominal time will be presented to 3 significant figures (i.e.: 0.0167, 0.050, 0.083, 0.167, 0.333, 0.500, and 0.667 hours postdose). After 0.667 h, time will be presented as 2 decimal places (i.e.: 1.00, 2.00, 4.00, 8.00, 12.00, 24.00, 36.00, and 48.00 hours postdose).

6.2.11. PK Parameters

Concentration-time data for PK10571 will be analyzed using noncompartmental methods in PhoenixTM WinNonlin[®] (Version 6.3 or higher, Certara, L.P.)¹.

During the pharmacokinetic analysis, concentrations that were BLQ up to the time of the first quantifiable concentration will be treated as zero. Embedded (values between 2 quantifiable concentrations) and terminal BLQ concentrations will be treated as "missing". Actual sample times will be used in the pharmacokinetic analysis.

The following PK parameters will be calculated for PK10571 for single ascending dose (SAD, Part A):

Parameter	Definition
C _{max}	Maximum plasma concentration, determined directly from individual concentration-time data, reported to 3 significant figures
	C_{max} will be presented with and without weight-adjustment. Weight adjustment will be calculated as C_{max} x body weight in kg/70.
T _{max}	Time of the maximum plasma concentrations, reported to 2 decimal places
C _{last}	Last quantifiable plasma concentration determined directly from individual concentration-time data, reported to 3 significant figures

Parameter	Definition
T _{last}	Time of last quantifiable plasma concentration, reported to 3 significant figures
AUC ₀₋₂₄	Area under the plasma concentration-time curve from time-zero to 24 hours postdose, reported to 3 significant figures AUC ₀₋₂₄ will be presented with and without weight-adjustment. Weight adjustment will be calculated as AUC ₀₋₂₄ x body weight in kg/70.
AUC _{last}	Area under the plasma concentration-time curve from time-zero to the time of the last quantifiable concentration (C_{last}), as calculated by the linear trapezoidal method, reported to 3 significant figures $AUC_{last} \ will \ be \ presented \ with \ and \ without \ weight-adjustment. \ Weight \ adjustment \ will \ be \ calculated \ as \ AUC_{last} \ x \ body \ weight \ in \ kg/70.$
AUCinf	Area under the plasma concentration-time curve from the time of dosing extrapolated to infinity, reported to 3 significant figures and calculated as: $AUC_{0\text{-inf}} = AUC_{0\text{-last}} + C_{last}/\lambda z, \text{ where } \lambda z \text{ is the apparent terminal elimination rate constant calculated by linear regression of the terminal linear portion of the log concentration versus time curve AUC_{inf} \text{ will be presented with and without weight-adjustment. Weight adjustment will be calculated as } AUC_{inf} \text{ x body weight in kg/70.}$
$\lambda_z (K_{el}, Lambda z)$	Apparent terminal elimination rate constant calculated by linear regression of the terminal linear portion of the log concentration versus time curve, reported to 3 significant figures
T _½	The observed terminal elimination half-life, reported to 3 significant figures and calculated as: $T_{1/2} = \ln(2)/\lambda_z$
CL/F	The apparent total plasma clearance after an inhaled dose, reported to 3 significant figures and calculated as:

Parameter	Definition
	CL/F=Dose/AUC _{0-inf} , where F is the bioavailability
	CL/F will be presented with and without weight-adjustment. Weight adjustment will be calculated as CL/F x 70/body weight in kg.
	The apparent volume of distribution after an inhaled dose, reported to 3 significant figures and calculated as:
V_z/F	$V_z/F=Dose/(AUC_{inf} \times \lambda_z)$, where F is the bioavailability
	Vz/F will be presented with and without weight-adjustment. Weight adjustment will be calculated as Vz/F x 70/body weight in kg.

The following PK parameters will be calculated for PK10571 for multiple ascending dose on Days 1 and 7, unless specified otherwise (MAD, Part B):

Parameter	Definition
C _{max}	Maximum plasma concentration, determined directly from individual concentration-time data, presented to 3 significant figures
	C_{max} will be presented with and without weight-adjustment. Weight adjustment will be calculated as C_{max} x body weight in kg/70.
T_{max}	Time of the maximum plasma concentrations, presented to 3 significant figures
Clast	Last quantifiable plasma concentration determined directly from individual concentration-time data, presented to 3 significant figures
T _{last}	Time of last quantifiable plasma concentration, presented to 3 significant figures
AUC ₀₋₂₄	Area under the plasma concentration-time curve for time zero to 24 hours postdose, presented to 3 significant figures

Parameter	Definition	
	AUC ₀₋₂₄ will be presented with and without weight-adjustment. Weight adjustment will be calculated as AUC ₀₋₂₄ x body weight in kg/70.	
Cavg,ss	Average concentration at steady state, calculated as AUC ₀₋₂₄ /24 h (Day 7 only), presented to 3 significant figures	
CLss/F	Apparent clearance at steady state (Day 7 only), presented to 3 significant figures and calculated as:	
	CLss/F=Total daily dose/AUC ₀₋₂₄ , where F is the bioavailability.	
	CLss/F will be presented with and without weight-adjustment. Weight adjustment will be calculated as CLss/F x 70/body weight in kg.	
V _z /F	Apparent volume of distribution in the terminal phase (Day 7 only), presented to 3 significant figures	
	Vz/F will be presented with and without weight-adjustment. Weight adjustment will be calculated as Vz/F x 70/body weight in kg.	
Rac	Accumulation ratio during multiple dosing; presented to 3 significant figures and calculated as:	
	RAC=AUC ₀₋₂₄ Day 7/AUC ₀₋₂₄ Day 1	
$\lambda_z \left(K_{el} , \right. \\ Lambda z)$	Apparent terminal elimination rate constant calculated by linear regression of the terminal linear portion of the log concentration versus time curve (Day 7 only), presented to 3 significant figures	
Т½	The observed terminal elimination half-life, presented to 3 significant figures and calculated as:	
	$T_{1/2} = \ln(2)/\lambda_z$ (Day 7 only)	

No value for λ_z and other λ_z -related parameters (AUC_{inf}, $T_{1/2}$, etc.) will be reported if λ_z cannot be estimated.

PK concentration data will be summarized by study part, treatment, and day (for MAD study part) at each nominal sample time. PK parameter data will be summarized by study part, treatment, and day (for MAD study part). PK parameter data will also be stratified by sex and for males and females combined. PK parameter tables will include columns for baseline BMI, FEV1, and FVC.

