## APPENDIX 4 PART B: MAD TWICE DAILY (BID) DOSING

The Safety Review Committee will review the safety data (including local irritation) and pharmacokinetic data from the SAD protocol (Part A) to determine the starting dose for the first MAD cohort and if the first cohort of the MAD protocol should be dosed QD (once daily), BID (twice daily; once every 12 hours), or TID (three times daily; 6 hours between each dose for a given day of dosing).

If the decision is made to start dosing in the MAD protocol at BID, then the Safety Review Committee will review the safety data (including local irritation) and PK data from the first MAD cohort to determine if BID dosing should continue, if dosing should be reduced to QD, or if dosing should be increased to TID for the next cohort.

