Data from the lower dose cohort will be analyzed before deciding whether to proceed with the higher dose cohort. Alternately, a lower dose may be administered, depending upon review of the previous cohort's safety and pharmacokinetic data.

Subjects will receive one of the treatments listed below in randomized fashion.

Table 2 Part B: Planned Doses for Cohorts 1, 2 and 3

Cohort	Test Formulation (n = 6)	Placebo (n = 2)	
1	PK10571 initial dose	Placebo	OCHRESCO CONTRACTOR
2	PK10571 middose*	Placebo	
3	PK10571 high dose*	Placebo	

n = number of subjects

Note: Each subject will receive a dosing according to the assigned treatment either once daily (QD), twice daily (BID), or three times daily (TID) for 7 consecutive days. For TID dosing, each daily administration will be separated by 6 hours.

* Alternately, Cohort 2 or 3 will receive a lower dose, depending upon safety and pharmacokinetic data from Cohort 1 or 2, respectively.

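### On BID or TID days the SAP deletes a BLQ trough between doses, so Part B AUC0-24 can be inflated if those troughs fall below the assay limit

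*SAP*

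**What the plan says.** SAP 6.2.11 gives one BLQ rule for the noncompartmental analysis, placed before both the Part A and the Part B parameter tables:

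- Leading values: "concentrations that were BLQ up to the time of the first quantifiable concentration will be treated as zero".
- All others: "Embedded (values between 2 quantifiable concentrations) and terminal BLQ concentrations will be treated as" missing.

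The Part B table defines AUC0-24 as one area from time zero to 24 h, whatever the regimen. It gives no separate handling for a trough between doses and no integration rule for AUC0-24.

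The sampling grids are in SAP 6.2.10. For BID, samples are taken at "times after each dose (2 per day) on Day 1 and Day 7: 3 and 30 minutes and 2, 8, and 12 hours"; for TID, at "times after each dose (3 per day) on Day 1 and Day 7: 3 and 40 minutes and 6 hours". Protocol Appendix 4 describes "BID (twice daily; once every 12 hours", and the SAP Introduction states "For TID dosing, each daily administration will be separated by 6 hours". The 12 h (BID) and 6 h (TID) samples are therefore the troughs immediately before the next dose.

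For the concentration tables only, SAP 6.2.10 uses a different convention: "For summarization of the concentration-time data, concentrations below the limit of quantitation (BLQ) will be set to zero".

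**The concern.** After a single dose, a BLQ value between two quantifiable ones is an oddity, and dropping it does little harm. On a BID or TID day a BLQ trough is real information that the concentration fell below the assay limit. It counts as embedded only because the next dose raises the concentration again. Once it is deleted, the trapezoid joins the last quantifiable value of one dose to the early post-dose value of the next. That bridge spans about 5.4 h for TID (40 min to 6.05 h) and about 10 h for BID (2 h to 12.05 h) when both the 8 h and 12 h samples are BLQ.

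The rule also treats like troughs differently. A BLQ predose value on Day 7 is leading and counts as zero; a BLQ trough 6 or 12 h later is embedded and is deleted.

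AUC0-24 feeds Cavg,ss (AUC0-24/24) and CLss/F (daily dose/AUC0-24) in SAP 6.2.11, and the Part B power model in SAP 6.11. Interim PK parameters go to the Safety Review Committee (SAP 7), and Protocol 3.4 lists AUC among the dose-escalation factors. If only the lower-dose cohorts have BLQ troughs, only their AUC is inflated and the dose-proportionality slope is biased downward.

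**Working it through.** The plan gives no AUC, LLOQ or half-life, so there is no figure to reproduce. The check applies the SAP rule to assumed profiles on the SAP's own grids.

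**Assumptions.** One compartment, absorption rate ka = 20/h, half-life 1, 2 or 4 h, LLOQ 1, 2, 5 or 10% of single-dose Cmax, Day 1, no noise. Linear trapezoid (the SAP names it only for Part A AUClast), stopped at the last quantifiable sample. Each dose contributes C(t) = [ka/(ka − ke)]·[exp(−ke·t) − exp(−ka·t)], with ke = ln 2/half-life.

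**TID, half-life 1 h.** True area = 3/0.6931 = 4.328. Concentrations are 0.6195 (0.05 h), 0.6526 (0.667 h), 0.0162 (6 h), 0.6352 (6.05 h), 0.6628 (6.667 h), 0.0164 (12 h), 0.6354 (12.05 h), 0.6629 (12.667 h) and 0.0164 (18 h). The troughs are BLQ once the LLOQ is 2% of Cmax (0.02 × 0.886 = 0.0177) or more.

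- SAP rule, first bridge: 5.383 × (0.6526 + 0.6352)/2 = 3.466. Second bridge: 5.383 × (0.6628 + 0.6354)/2 = 3.494.
- Total: 0.016 + 0.392 + 3.466 + 0.400 + 3.494 + 0.400 = 8.17 after rounding; 8.17/4.328 = **1.89**.
- Between-dose troughs set to zero: the bridges become 5.333 × 0.6526/2 + 0.05 × 0.6352/2 = 1.756 and, likewise, 1.783. Total 4.75; ratio 1.10.
- Last interval also closed with zero at 18 h: add 5.333 × 0.6629/2 = 1.768. Total 6.52; ratio 1.51.

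**BID, half-life 1 h.** True area = 2/0.6931 = 2.885. Concentrations are 0.6195 (0.05 h), 0.7324 (0.5 h), 0.2590 (2 h), 0.0040 (8 h), 0.0003 (12 h) and 0.6198 (12.05 h). The 8 h and 12 h values are BLQ at every LLOQ tried.

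- SAP rule, bridge: 10.05 × (0.2590 + 0.6198)/2 = 4.416. Total: 0.016 + 0.304 + 0.744 + 4.416 + 0.304 + 0.744 = 6.53; ratio **2.26**.
- Between-dose values zero: the bridge becomes 6 × 0.2590/2 + 0.05 × 0.6198/2 = 0.793. Total 2.90; ratio 1.01.
- Last interval also closed: add 0.777. Total 3.68; ratio 1.28.

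**Ratio to true AUC0-24 where the rule has an effect**

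| Setting | SAP rule | Between-dose BLQ = 0 |
|---|---|---|
| TID, 1 h, trough BLQ | 1.89 | 1.10 |
| BID, 1 h, 8 h and 12 h BLQ | 2.26 | 1.01 |
| BID, 2 h, LLOQ 2-5% (12 h BLQ) | 1.33 | 1.11 |
| BID, 2 h, LLOQ 10% (8 h and 12 h BLQ) | 1.49 | 0.75 |

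**No effect** (both rules give the same area): TID at 2 h for LLOQ 1-10%; TID at 1 h and BID at 2 h for LLOQ 1%; both regimens at 4 h for LLOQ 1-10%; and QD, which has no second dose within 24 h.

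**How much is due to the BLQ rule.** The grids are sparse, so a straight line over a steep decline overstates the area under any BLQ rule. Against zero in every interval, the SAP rule inflates AUC0-24 by 8.17/6.52 = 1.25 (TID, 1 h) and 6.53/3.68 = 1.77 (BID, 1 h).

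**Other shapes and integration rules.** With instantaneous peaks and with bi-exponential decline, half-lives of 0.5 to 4 h and LLOQ 1-20% of peak, the SAP rule gave 1.2 to 2.2 times (TID) and 1.3 to 3.4 times (BID, 8 h and 12 h BLQ) the area with all samples known. Linear-up/log-down did not remove the excess over the true area: 1.4 to 3.9 (TID) and 1.4 to 4.4 (BID).

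**Day 7 against Day 1.** Where the rule has an effect, both days are inflated alike. At 1 h, Rac is 1.000 true and 1.000 under the SAP rule; for BID at 2 h it is 1.008 true and 1.007 to 1.008 under the rule.

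**The case against.** The strongest reply is that the premise may never arise. BID and TID are conditional options (Protocol 3 and 3.2). The plan regresses Day 3-7 troughs, estimates a Day 7 half-life and samples to Day 35, which suggests that quantifiable troughs were expected. Doubling appears only at a half-life near 1 h, and several settings show no effect at all. This stands as a limit on size and likelihood. It does not make the rule right when a trough is BLQ, and nothing in the documents excludes that case.

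Two stronger readings are tempting, and neither is supported.

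- A reader might infer that Rac and the Day 7 to Day 1 comparison are pulled down. That needs troughs that are BLQ on Day 1 but quantifiable on Day 7. At the short half-lives where the rule has an effect, accumulation is negligible and the inflation cancels: Rac under the SAP rule stayed within 0.003 of true values of 1.00 to 1.04. Protocol 1.1.1 also reports that accumulation did not appear to be an issue in rats or dogs.
- A reader might infer that the SAP contradicts itself because "concentrations below the limit of quantitation (BLQ) will be set to zero" in 6.2.10 while 6.2.11 deletes them. The first rule is limited to summarising concentrations and the second to the PK analysis. Different handling is explicit and is not in itself an error.

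Zero is not a perfect substitute either. For BID at 2 h with LLOQ 10% of Cmax, zeroing only the between-dose values gives 0.75 of the true area, a 25% understatement.

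**Conclusion.** The concern holds conditionally. SAP 6.2.11 as written deletes a BLQ trough between doses and replaces it with area interpolated up to the next post-dose sample. Under the stated assumptions AUC0-24 comes out at 1.9 (TID) to 2.3 (BID) times the true value at a 1 h half-life, and 1.3 to 1.5 times for BID at 2 h with LLOQ 2-10% of Cmax. Cavg,ss rises by the same factor. CLss/F falls to 1/1.89 = 0.53 (TID) or 1/2.26 = 0.44 (BID) of its true value at 1 h. The effect is nil with QD dosing or when the between-dose troughs are quantifiable. The documents do not support a general claim that AUC is doubled. Which case applies depends on a half-life and an LLOQ that the documents do not state. Because the correction is cheap and AUC is used between cohorts, it is worth making before any BID or TID cohort is analysed.

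**What to change.** In SAP 6.2.11:

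1. Limit the embedded-BLQ-as-missing rule to a BLQ value followed by a quantifiable value within the same dosing interval.
2. For BID and TID days, define AUC0-24 as the sum of the dosing-interval AUCs. Set BLQ values after the last quantifiable value of an interval, including the sample just before the next dose, to zero.
3. Apply this identically to every interval within 0-24 h on Day 1 and Day 7, including the last one.
4. Keep terminal BLQ as missing for lambda-z.
5. Name the trapezoid rule for Part B AUC0-24; segments that end at zero have to be linear.
6. Add a sensitivity analysis with LLOQ/2 in place of zero.

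Item 3 matters. If zero applied only where another dose follows, the last interval would be closed on Day 1 but not on Day 7. A true Rac of about 1.00 would then become 2.90/3.68 = 0.79 (BID, 1 h) or 4.75/6.52 = 0.73 (TID, 1 h).

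The cost is a short SAP amendment, a change to the NCA template and one extra sensitivity table. The downside is that zero can understate AUC when troughs lie just below the LLOQ, which the sensitivity analysis would show. The change does not cure sparse sampling: for TID at 1 h the area remains about 1.5 times the true value (6.52/4.328).

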#### 8.2 Pharmacokinetic Analysis

Pharmacokinetic parameters for PK10571will be calculated using non-compartmental analysis. The following pharmacokinetic parameters will be determined:

The maximum plasma concentration ( $C_{max}$ ) and time to  $C_{max}$  ( $T_{max}$ ) will be taken directly from the data. The elimination rate constant,  $\lambda_z$ , will be calculated as the negative of the slope of the terminal log-linear segment of the plasma concentrationtime curve; the range of data to be used will be determined by visual inspection of a semi-logarithmic plot of concentration vs. time. Elimination half-life ( $T_{1/2}$ ) will be calculated according to the following equation:

 $T_{\frac{1}{2}} = 0.693 / \lambda_Z$ 

Area under the curve to the final sample with a concentration greater than the limit of quantitation (LOQ), (AUClast), will be calculated using the log trapezoidal method and extrapolated to infinity using:

 $AUC_{inf} = AUC_{last} + C_{last} / \lambda_Z$ 

where  $C_{last}$  is the final concentration  $\geq LOQ$ .

All evaluable subjects will be included in the pharmacokinetic analysis. Pharmacokinetic calculations will be performed using appropriate software, e.g. PhoenixTM WinNonlin® (Version 6.3 or higher, Pharsight Corporation) and/or SAS® (Version 9.3 or higher, SAS Institute Inc.).

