#### 8.3 Statistical Analysis

Comparison of the log-transformed pharmacokinetic parameters Cmax, AUClast, and AUCinf for PK10571across treatments will be performed using an ANOVA model and the two one-sided t-tests procedure. The ANOVA model will include factors for subject, treatment, and cohort. The ratios of the geometric means and 90% confidence intervals will be reported. Statistical analyses will be performed using appropriate software, e.g. PhoenixTM WinNonlin® (Version 6.3 or higher, Pharsight Corporation) and/or SAS® (Version 9.4 or higher, SAS Institute Inc.). Additional details regarding statistical analysis will be provided separately in the statistical analysis plan (SAP).

Gossamer Bio, Inc.

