8. CHANGES TO PLANNED PROTOCOL ANALYSIS

No changes planned to protocol analysis.

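### SAP section 8 declares no changes, but the SAP switches Part A AUClast from the log to the linear trapezoidal rule and replaces the protocol 8.3 ANOVA

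*SAP*

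**What the plan says.** **AUC rule.** Protocol 8.2, which is not limited to one study part, says AUClast "will be calculated using the log trapezoidal method and extrapolated to infinity". SAP 6.2.11, in the Part A parameter table, defines AUClast "as calculated by the linear trapezoidal method". The same table builds AUCinf on AUClast, and CL/F and Vz/F on AUCinf. For values below quantitation, SAP 6.2.11 says that "concentrations that were BLQ up to the time of the first quantifiable concentration will be treated as zero". It names no trapezoidal rule for AUC0-24.

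**Comparison.** Protocol 8.3 says that the comparison of log Cmax, AUClast and AUCinf across "treatments will be performed using an ANOVA model and the two one-sided t-tests procedure". It adds: "The ANOVA model will include factors for subject, treatment, and cohort" and "The ratios of the geometric means and 90% confidence intervals will be reported". SAP 6.11 has no such comparison. It has a Part B ANOVA of log Cmax and AUC0-24 on Day 7 against Day 1, with subject, day and cohort as factors, the two one-sided tests wording, and 95% intervals. It also has a power model for dose proportionality, with a 95% interval for the slope.

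**Declaration.** SAP section 8 reads in full: "No changes planned to protocol analysis".

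**The concern.** Section 8 is where a reader looks to learn how the SAP departs from the protocol, and here it reports no departure. On the AUC rule the documents give opposing instructions, so absolute Part A AUClast, AUCinf, CL/F and Vz/F depend on which one the analyst follows. On the comparison, a reader of the protocol would expect geometric mean ratios between dose levels with 90% intervals. Those ratios will not be produced, and the model meant to produce them does not suit the design.

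**Working it through.** **1. AUC rule**

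Inputs from the documents: the Part A sampling grid (predose; 3, 10, 20, 30 and 40 min; 1, 2, 4, 8, 12, 24, 36 and 48 h), with a first sample at 5 min for multi-capsule doses, or at 1 and 5 min before the protocol amendment (SAP 6.2.10).

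Assumed, because neither document gives them: absorption half-life 1.5 min, mono-exponential decline with a half-life of 1 to 24 h, and a quantitation limit of 0.1% or 1% of Cmax.

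Over an interval of length d from concentration C1 to C2:
- linear: d × (C1 + C2)/2
- log: d × (C1 − C2)/ln(C1/C2), undefined if either value is zero

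On an exponential decline with rate k, put x = k × d. The linear/log ratio is then (x/2)/tanh(x/2). For one of the 12 h gaps after 12 h:

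| Half-life | x = 12 × ln2 / half-life | linear/log |
|---|---|---|
| 4 h | 2.079 | 1.34 |
| 6 h | 1.386 | 1.16 |
| 12 h | 0.693 | 1.04 |
| 24 h | 0.347 | 1.01 |

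The late gaps carry only part of the area, so the effect on the whole AUClast is smaller. Over the full grid (log rule, made linear where a value is zero; 3-min first sample):

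| Half-life | linear over log, AUClast (limit 1% / 0.1%) |
|---|---|
| 1 h | +4.4% / +7.6% |
| 4 h | +5.6% / +6.0% |
| 6 h | +4.5% / +4.6% |
| 12 h | +2.0% / +2.0% |
| 24 h | +0.6% / +0.6% |

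- The other first-sample schedules raise the maximum to 7.8%. AUClast is therefore about 0.6 to 8% higher with the linear rule.
- AUCinf = AUClast + Clast/λz is 0.5 to 7.7% higher. CL/F and Vz/F, which divide by it, are 0.5 to 7.2% lower (1 − 1/1.077 = 0.072).
- Against the exact integral of the assumed curve, linear AUCinf is 0.4 to 7.0% too high. Log and linear-up/log-down are both within about 1%.
- Power-model slope: with relative doses 1, 2, 4, 8, 12 (protocol 3.4 multiples; the first step is not legible and is assumed 2-fold) and a limit of 0.1 to 5% of the lowest-dose Cmax, linear instead of linear-up/log-down moves the slope by at most 0.017.

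**2. Protocol 8.3 model**

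Inputs: 6 active subjects per cohort, one cohort per subject (protocol section 3), and a PK population of active subjects only (SAP 6.1.2). Each cohort has one active dose, so in the PK data treatment is a function of cohort.

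- Part A, subject and cohort fixed: 5 × 6 = 30 values, model rank 30, error df 30 − 30 = 0. With 4 cohorts: 24 − 24 = 0. No treatment contrast is estimable.
- Part A, subject random and cohort fixed: treatment + cohort has rank 5, and cohort alone has rank 5. Treatment adds 5 − 5 = 0 and is fully aliased.
- Part B gives rank 3 and 3. Using both days (36 records) leaves 36 − 18 = 18 error df, but treatment is still not estimable.
- With dose level as the only factor, Part A would have 30 − 5 = 25 error df (24 − 4 = 20 with 4 cohorts), and the ratios would be estimable.

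**3. SAP Day 7 versus Day 1 model**

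Pooled over three cohorts: 36 records, rank 19, 17 error df, day effect estimable. Per cohort: 12 − 7 = 5 error df. Cohort is nested in subject, so it adds nothing to the pooled model and has a single level in a per-cohort run.

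**4. Version check**

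The SAP cites protocol version 5.0. The 5.0-to-5.3 change list in protocol Appendix 6 has no entry for section 8, and SAP 6.2.10 already carries the version 5.3 sample counts. The version gap does not explain the differences.

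**The case against.** **Detail was delegated.** Protocol 8.3 leaves further statistical detail to the SAP, SAP 3.1 lists dose linearity and steady state as PK endpoints, and an analyst would normally follow the SAP. In practice this limits the confusion. It does not make an opposite AUC rule, or a different contrast, a detail.

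**The inestimability argument has a limit.** Protocol 8.3 does not say which factors are fixed. If cohort were random, dose-level mean ratios could be computed, although cohort variance could not be separated with one cohort per dose. This stands: the result covers cohort as a fixed factor, with subject either fixed or random.

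**The effect is small.** At a 24 h half-life the AUClast gap is about 0.6%, and every percentage rests on assumed kinetics. This also stands and keeps the point modest.

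Three stronger readings are not supported:
- A reader might take 90% and 95% as conflicting levels for the same interval. They belong to different contrasts. The leftover is wording: two one-sided tests at 5% per side pair with a 90% interval, but no margin or alpha is stated.
- A reader might extend the linear rule's error to AUC0-24 on the sparse BID and TID grids. The SAP names no rule for AUC0-24, so this is a gap to fill and not a demonstrated bias.
- A reader might infer that the Day 7 versus Day 1 model gives only one ratio common to all cohorts. Tables 14.4.15 to 14.4.17 and Listings 16.2.6.8 to 16.2.6.10 are set out by cohort, which suggests separate runs. The SAS code that would settle this is not in the available text.

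**Conclusion.** The point holds in this limited form: SAP section 8 is inaccurate in two respects, and both should be corrected. The contradiction between the AUC rules is plain on the text. Its size depends on the kinetic assumptions above. That the protocol 8.3 model cannot give treatment ratios with cohort fixed is algebra and needs no kinetic assumption. Replacing that model was reasonable; the fault is that the replacement is not declared. Nothing here shows that dose-proportionality, safety or escalation conclusions would change. This is a correction that should be made, not one on which the trial's findings turn.

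**What to change.** - State one AUC rule in protocol 8.2 and SAP 6.2.11 and apply it to every AUC, including AUC0-24. A rule that is logarithmic on the declining phase and linear where a value is zero or rising keeps the protocol's intent, is defined when early values below quantitation are set to zero, and avoids the linear rule's upward bias. Either stated rule would also reconcile the documents, provided the log rule's first interval is defined.
- Replace the protocol 8.3 model with the SAP 6.11 analyses. Either drop the two one-sided tests wording and keep the 95% intervals as descriptive, or keep it and report 90% intervals.
- List and briefly justify these changes in SAP section 8.
- As a query only: confirm from the SAS code that Day 7 versus Day 1 is run separately by cohort. If so, remove the redundant cohort factor from the text.

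The cost is wording in SAP 6.2.11, 6.11 and 8 and in protocol 8.2 and 8.3, plus one software setting. The downside is recalculation of any AUC, and of the CL/F and Vz/F derived from it, already computed under another rule.
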